### **8.3 Follow-up**

Participants will be scheduled for a Test of Cure (TOC) follow up visit 4 weeks after treatment completion with a window of 3-12 weeks post-baseline for the 2 gm MTZ dose and 4-13 weeks post-baseline for the 7 day MTZ dose. Prior to the follow-up visit, women will be contacted by study staff via their preferred method (i.e., cell phone, text message, or email) to remind them of their study visit. If they miss their scheduled visit, study staff will attempt contact at least five times. All contact attempts will be noted in the participant's file.

At follow-up visits, she will undergo the ACASI survey, and testing for TV and BV. For specimen collection, women will be reminded of vaginal self-swab procedures and asked to collect up to five vaginal swabs, place them in the sterile tubes and return to study office. Study staff will place one swab in the InPouch, one in the FMS tube, one for NAAT and use the other swab to prepare a Gram stain slide as described above. For sites that will perform a wet prep at TOC, a swab will be prepared for wet prep and read by the study staff. Specimens will be labeled with study identification number and date of collection. Procedures for processing these specimens and reporting of results will be same as described for baseline procedures. Any positive InPouch or wet prep will be reported to the participant's provider at the clinic to arrange for treatment. The study does not provide medication for participants after baseline enrollment and initial treatment. In the case of a TV positive result at follow up, clinical staff will provide treatment in accordance with clinic protocols. Gram stain results are for study evaluation only and will not be used as a diagnostic tool for providers. After completion of visit, participant will receive \$50 compensation; contact information and preferred methods of

Version: 11.0

Version date: 1/2/17

If a woman is TV positive by InPouch culture at her TOC visit, she will have concluded her follow up visits. If, however, a woman is TV negative by InPouch but TV positive by NAAT testing, she may be asked to return for a follow-up visit 4 weeks post TOC visit (3-8 weeks after her TOC visit) for further evaluation. At the follow-up visit 4 weeks post TOC, she will be asked to self-collect up to five vaginal swabs and complete an ACASI survey as in her TOC visit. She will be given \$50 compensation and contact information and preferred methods of contact will be updated. If she tests TV positive by InPouch at this visit, results will be provided to clinical staff in order for her to receive treatment as standard clinical protocol.

### **8.4 Final Study Visit**

The final study visit will either be the TOC visit at 4 weeks post treatment completion or a follow-up visit 4 weeks post TOC visit (if she was NAAT+/InPouch- at her TOC visit and asked to return).

### **8.5 Early Termination Visit**

After providing informed consent and undergoing randomization, it is possible that a woman will refuse the intervention. If this happens, she will still receive her baseline compensation for dedicating time to the study up to that point (the randomization is near the end of the baseline visit). She will be referred back to her clinician for treatment of TV as per clinical protocol. Her self-collected vaginal swabs will be discarded.

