If a participant's clinical TV positive test result is not confirmed TV-positive by InPouch culture or NAAT, she will be withdrawn from the study. These testing procedures and de-enrollment potential will be fully explained in the consent form. Women will receive \$20 compensation after completion of the baseline enrollment visit. Women will receive a study contact card that has all contact information for study personnel so that she may contact staff in case of appointment change, questions, or adverse events. She will be instructed to keep this card during the course of the study period. If she is withdrawn, she will keep her baseline compensation but told she will not need to attend her follow-up visits.

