## **9.10 Stopping Rules for an Individual Participant/Cohort**

Criteria for Discontinuation of Study Agent(s)/Intervention(s):

-if they are randomized to an arm and are unable to tolerate the dose the study agent will be discontinued.

Criteria for Withdrawal of a Participant:

-if they become incarcerated and are unable to attend follow up visits

-if any clinical adverse event, laboratory abnormality, concurrent illness, other medical condition or situation occurs such that continued participation in the study would not be in the best interest of the participant.

-if a woman is found to be pregnant after consent but prior to randomization

-if a woman is found to be ineligible after consent but prior to randomization

-if a participant initial TV positive wet prep result is not confirmed by either InPouch culture or TV NAAT test from her enrollment visit

Version: 11.0

Version date: 1/2/17

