## **11.4 Measures to Minimize Bias**

### **Enrollment/ Randomization/ Masking Procedures**

After eligibility is assessed, informed consent is obtained and the woman has completed the ACASI survey and self-swab collection, she will be randomized to treatment arm. A blocked randomization scheme will be used to avoid “runs” in the randomization process. Each site will have its own blocked randomization scheme. Pre-numbered, sealed envelopes will be selected sequentially and opened for each participant who will then be enrolled in the indicated treatment arm. Because we are conducting a phase III trial and behaviors associated with the interventions are important, we will not attempt to make the single dose mimic a 7-day dose by supplementing with placebo. The trial will, therefore, be un-blinded. There will be no replacement of participants who discontinue early. Enrollment will continue through two months prior to study end.

Study personnel will know which arm the participant was randomized to. This information will not be disclosed to laboratory personnel. The Program Manager will periodically ensure that all participants were randomized to the correct treatment arm as indicated in the randomization scheme. Any discrepancies will be immediately discussed with investigators to prevent further error.

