## 11.8 Maintenance of Trial Treatment Randomization Codes

Randomization will occur at the end of each baseline study visit. Randomization codes will be determined by a block randomization strategy at each site. Sealed envelopes will contain a study identification number on the outside and the randomization arm on the inside. Study staff will chose randomization envelopes sequentially and only open the card after enrollment, survey and specimen collection has occurred. There will be a separate staff member who will create and number the envelopes thereby shielding clinic study staff from knowing the randomization scheme. No study staff at the clinic will have access to the randomization database or numbering scheme. Every six months, a randomization interim analysis will be performed by Tulane staff for DSMB review to ensure that the randomization strategy is successful. The randomization arm will be noted on the study file and in the participant's data once the baseline visit is completed. No laboratory or clinical staff will have access to the randomization database.

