### **11.13 Final Analysis Plan**

Analyses will be conducted in an intent-to-treat manner with variables categorized per protocol. To assure that randomization has been achieved, selected demographic, clinical and behavioral (including medication adherence and sexual re-exposure) factors will be compared by study arms using chi-square, t-test or ANOVA, where applicable. If randomization was found to be successful (as indicated by even distribution of potential confounders) then analyses will be conducted with no need to adjust for confounding. If randomization was not achieved, then associations will be explored for potential confounding and if found these factors will also be included in the model. From the two aims, there are two hypotheses:

H1: Women receiving multi-day MTZ will be less likely to test TV positive at TOC compared to women who receive the single dose MTZ.

H2: This effect (H1) will only be observed among women who have BV (Nugent score  $\geq 7$ ).

Analysis: The research questions will be answered using a multivariable logistic regression analysis to examine the effect of single versus multi-dose (H1) and the differential impact of BV on this effect (H2). This primary logistic model contains two main effects (i.e. treatment and BV)

Version: 11.0

[figure not shown]
Version date: 1/2/17

and 1 first order interaction (BV by index treatment)). The model (1) will be:  $g(Y_i) = \beta_0 + \beta_1 + \beta_2 + \beta_1 \cdot \beta_2$  where:  $g(Y_i) = \log$  odds of repeat infection,  $\beta_0 =$  coefficient for the intercept,  $\beta_1 =$  (Factor 1) single versus multi-dose,  $\beta_2 =$  (Factor 2) BV at time of visit

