All analyses will be conducted in SAS by Tulane staff under the direction of [name]. Because we will use strict protocols and employ tight supervision of the study sites and the study populations are similar (mostly African American and underserved) we do not anticipate site variations but we will examine for any differences and if found, we will include a site variable in the models. We do not anticipate a three-way interaction, and our simulations (see below) support that belief. We will, however, run a fully parameterized model including all main effects, first order interactions, and second order interaction before running the primary analysis model (1) above. We will consider any p-value less than 0.05 to be significant and any p-value less than 0.10 as near-significant. If there is unexpected significant or near-significant interaction, we will stratify on BV status and assess the impact of index treatment (single vs. multi-dose) and any possible interaction separately for BV positive and BV negative women.

Additional analyses– The ACASI will allow for examination of index adherence to medication, index knowledge of partner treatment, sexual exposure and the nature of the sexual act and sexual partner, condom use. These factors will be assessed by arm to determine if any confounding occurred and if so, these analyses will be adjusted for these factors or stratified by these factors.

**Figure 4:** Algorithm for determining origin of repeat infection at TOC

**Outcome measures** – The study is powered for repeat infections. Since we will have information on sexual exposure and genotyping, we can also refine this outcome measure to examine treatment failure (H1 & H2) and reinfection and will use the algorithm depicted in figure 4.

All analyses will be conducted in SAS by the Tulane staff under the direction of [name]. As the data collection instruments are designed to

minimize missing data we do not anticipate an excessive amount. However, imputation techniques will be utilized to compensate for missing data (e.g. multiple imputation and maximum likelihood). Sensitivity analyses will be conducted to ensure that the method chosen to account for missing data does not bias the study’s results. Additionally, the characteristics of those who complete the study will be compared to those who drop out to determine whether drop out is informative. If not, multiple imputation methods will be used for initial analyses. If,

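### Section 8.5 discards the pre-randomisation swabs of women who refuse treatment after randomisation and describes no test-of-cure visit for them, which fits poorly with the declared intent-to-treat analysis; the likely effect is small

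*Combined protocol and SAP*

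**What the plan says.** All references are to the combined protocol and SAP.

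- **Refusal after randomisation.** Section 8.5 (Early Termination Visit) foresees that a woman may refuse the intervention after consent and randomisation. She is paid for baseline and referred to her clinician. Of her specimens it says: "Her self-collected vaginal swabs will be discarded". It mentions no TOC visit, but it does not forbid one.
- **Order of events.** Under Section 11.4, once "the woman has completed the ACASI survey and self-swab collection, she will be randomized to treatment arm". Section 11.8 likewise has staff "only open the card after enrollment, survey and specimen collection has occurred". The swabs therefore already exist when she learns her arm.
- **Blinding.** Section 11.4: "The trial will, therefore, be un-blinded".
- **What the swabs decide.** Under Section 8.2, if the clinic's positive result "is not confirmed TV-positive by InPouch culture or NAAT, she will be withdrawn from the study". Section 9.10 gives the same ground for withdrawal where the first result "is not confirmed by either InPouch culture or TV NAAT test from her enrollment visit". The Gram stain from the same visit gives the baseline Nugent score (Sections 7.2.2.2, 8.2 and 11.5).
- **Analysis.** Section 11.13: "Analyses will be conducted in an intent-to-treat manner". It defines no analysis set. Its primary model has treatment, BV and their interaction, with the BV term described as status at the time of the visit. On missing data it says "imputation techniques will be utilized to compensate for missing data", adds sensitivity analyses and a comparison of completers with drop-outs, and runs a complete-case analysis alongside. Post-randomisation refusers are not mentioned.
- **Withdrawal.** Section 9.11 keeps data already collected from women who withdraw. Sections 9.12 and 11.4 rule out replacement.

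**The concern.** Intent-to-treat protects the comparison because membership of the analysis cannot depend on anything that happens after the arm is known. Refusal does happen after that, and in an open-label comparison of one dose with seven days of treatment it may be commoner in one arm.

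Withdrawing women whose TV is not confirmed is harmless to the comparison as long as it rests on specimens taken before randomisation. Section 8.5 removes that safeguard for refusers. Once the swabs are gone, nobody can say whether such a woman was a confirmed case, and her baseline Nugent score is lost. If she also has no TOC visit, her outcome is unobserved. What is at stake is possible selection bias in the treatment difference. Lost precision is secondary.

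**Working it through.** **1. Planned figures (Section 11.7).** Rates are 16.2% (single dose) and 10.7% (7-day), power 0.80. A two-sided 0.05 pooled two-proportion formula without continuity correction gives

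n per arm = [1.96·√(2·0.1345·0.8655) + 0.8416·√(0.162·0.838 + 0.107·0.893)]² / 0.055² = (0.9457 + 0.4048)² / 0.003025 ≈ 603, or 1206 in total.

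1206 × 1.15 × 1.20 = 1664. Both stated figures reproduce. There are 832 women per arm (Section 6.1.1.1) and 1332 evaluable at TOC.

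**2. What is known about a refuser under Section 8.5.**

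| Item | Source in the plan | Status |
|---|---|---|
| Clinic TV result | 8.1 | kept |
| Baseline survey | 8.2 | kept, if 9.11 applies |
| Study TV confirmation | 8.2, 9.10 | lost with the swabs |
| Baseline Nugent score | 7.2.2.2, 11.5 | lost with the swabs |
| TV at TOC (primary endpoint) | 4.2.1 | probably unobserved; no visit described |
| BV at TOC | 11.5 | probably unobserved |

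**3. Size of a possible bias.** The documents give neither a refusal rate nor a failure rate among refusers, so both are assumptions. Let a fraction r of the 7-day arm alone refuse, let refusers fail at rate q, and let 10.7% be the rate among women who accept. Then:

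- Rate over all women randomised to 7 days = (1 − r)·10.7% + r·q
- Difference over all randomised = 5.5 − r·(q − 10.7) points
- Overstatement if refusers are left out = r·(q − 10.7) points

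Two values of q are used: 16.2% (the planned single-dose rate) and 30% (near the top of the 5% to 31% repeat-infection range quoted in Section 2.1).

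| r | Women (832·r) | q = 16.2%: true difference | Overstated by | q = 30%: true difference | Overstated by |
|---|---|---|---|---|---|
| 1% | 8 | 5.45 | 0.06 | 5.31 | 0.19 |
| 2% | 17 | 5.39 | 0.11 | 5.11 | 0.39 |
| 5% | 42 | 5.23 | 0.28 | 4.54 | 0.97 |

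If q = 10.7% the bias is zero. If refusal fell only in the single-dose arm and those women failed more often than 16.2%, the sign would reverse.

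**4. Power.** Taking the plan's 15% ICC inflation at face value, the effective size is 1332/1.15 ≈ 1158, or 579 per arm, and power at the planned rates is 0.784 (0.838 if the inflation is ignored). For the true differences above it is 0.775, 0.766 and 0.738 at q = 16.2%, and 0.752, 0.718 and 0.606 at q = 30%. As pure loss without bias, refusal by 5% of both arms on top of the planned follow-up loss moves power from 0.784 to 0.763.

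**5. What the figures measure.** Every figure in steps 3 and 4 comes from the missing TOC outcome. Keeping the swabs without a TOC visit would not change them. The harm from the discard itself, unknown case status and no baseline BV, is not quantified here.

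**The case against.** - **The rule is narrow.** Section 5.1.1 requires willingness to accept either arm. Under Sections 6.1.1.1 and 14.7, a woman who merely does not take her dose under observation stays in. The assumed 8 to 42 refusers compare with 1664 − 1332 = 332 losses already planned for. This stands, and it is why the point is minor.
- **The missing TOC is inferred.** Sections 5.2 and 8.3 schedule participants for TOC generally, with at least five contact attempts after a missed visit. This stands in part. A reader might infer that Section 8.5 bars follow-up; it does not. It is silent, under a heading that suggests her participation ends.
- **Missing-data methods are planned.** Section 11.13 offers imputation, a drop-out comparison, sensitivity analyses and a route for non-ignorable missingness. These can model her outcome. They cannot restore a discarded specimen or show whether she met the confirmation rule in Sections 8.2 and 9.10, and the complete-case analysis omits her.
- **The baseline score may not be the model covariate.** This stands. Section 11.13 ties BV to the time of the visit without saying which visit, so it cannot be asserted that the discard removes a term of the primary model.
- **Refusers are not untreated.** They are referred for clinic treatment, so a high failure rate among them is speculative. This stands; the 30% column is an upper illustration.
- **She may have withdrawn consent.** Section 8.5 speaks of refusing the intervention, not of withdrawing consent for specimens or data. The consent pages were not available for review.

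**Conclusion.** The inconsistency is real and the likely effect is small. Section 8.5 discards pre-randomisation specimens because of an act that follows knowledge of the arm. That does not sit well with intent-to-treat in Section 11.13 or with keeping collected data in Section 9.11.

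On the assumption that 1% to 5% of the 7-day arm alone refuse, leaving them out would overstate a 5.5-point difference by about 0.06 to 0.28 points if they fail at 16.2%, and by about 0.2 to 1.0 points if they fail at 30%. Refusal rate, one-sidedness and failure rate are all assumed, and there is no bias if refusers fail at the acceptors' rate.

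A reader might go further and infer that the plan formally excludes refusers, or that the primary result will be materially biased. The documents support neither. No text removes refusers from the analysis, the clinic result remains, and no figure suggests that refusal will be common or concentrated in one arm.

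**What to change.** 1. Reconcile Section 8.5 with Sections 9.11 and 11.13.
2. In Section 8.5, unless the woman withdraws consent for it, keep and test the baseline swabs and invite her to TOC.
3. In Section 11.13, define the intent-to-treat set as all randomised women with TV confirmed on pre-randomisation specimens, analysed in the arm assigned. State that refusers without an outcome are handled as missing under the methods already in that section.
4. Report the number of refusals by arm, including women whose specimens could not be used.

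The cost is a few sentences, plus testing and a TOC visit for a small number of women (8 to 42 if 1% to 5% of one arm refuse) using procedures already in the protocol. The consent form may need a line on specimens and follow-up after refusal. The change has to be made before specimens are lost, because they cannot be recovered at analysis. No change to clinical care is involved.

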### **8.6 Pregnancy Visit**

Women will not be enrolled if they are pregnant. If they become pregnant during the course of the study, it will not affect study enrollment because they would have already been treated for TV. If it is determined that the participant was pregnant at the time of treatment, the woman and her child will be followed according to the site specific regulatory requirements.

### **8.7 Unscheduled Visits**

Since the study is housed within the clinics, there may be times when a participant has a clinic visit and is not scheduled for a study visit. If this occurs and the participant inquires about completing their study visit during their clinic time, study staff will review the participants file to see if she is within her follow up window, if so, she can complete her follow up visit, if not, she will have to return at her scheduled date/time.

If a participant has persistent symptoms or other complaints and comes to the clinic for an unscheduled visit, she will be referred to the clinic staff by the study staff for medical evaluation

Version: 11.0

Version date: 1/2/17

and treatment. She will keep her regularly scheduled TOC visit and her interim clinic visit will be noted.

The following is a schedule of visits and subject compensation at each visit

**Study Visit Schedule**

Visit Number	When is it?	Acceptable window of time to complete	Compensation
Visit 1	Date subject enrolls in study	N/A	\$20
Visit 2	4-weeks after scheduled completion of the medicine	If 1-day dose: 3 weeks-12 weeks after visit 1	\$50
		If 7-day dose: 4 weeks-13 weeks after visit 1	\$50
Visit 3 *only if applicable	4-weeks after visit 2	3 weeks-8 weeks after visit 2	\$50

\*You may be scheduled for this visit **only** if the NAAT is positive **and** the culture is negative.

## 9. ASSESSMENT OF SAFETY

### 9.1 Specification of Safety Parameters

Metronidazole in the 2gm dose is an FDA approved treatment for TV. The 7 day 500mg BID dose is recommended in the CDC treatment guidelines for TV, however, is not currently FDA approved.

There are three main safety concerns:

- 1) Adverse drug reactions including, allergy, hypersensitivity reaction, or other adverse reaction to metronidazole, alcohol use within 24 hours of taking medication, and contra-indications with other medications.
- 2) Pregnancy in a woman who tested negative at entry.
- 3) That discussing their infection with partners may put participants at risk for verbal or physical abuse by disclosing their STI to their partners.

## 9.2 Definition of an Adverse Event (AE)

Vomiting within 2 hours of consumption of the medication with no other signs of allergic reaction to MTZ will not be considered an adverse event but will be documented. Adverse events include eye pain, sudden vision changes, sore throat, persistent fever, unusual bleeding/bruising, severe stomach pain, persistent nausea/vomiting, fatigue, hypersensitivity reaction or other adverse reaction to MTZ.

Any form of intimidation, verbal or physical abuse will be considered an adverse event.

